2.9.3 Treatment Satisfaction Questionnaire for Medication

The Treatment Satisfaction Questionnaire for Medication (TSQM) is used to assess participant convenience and global satisfaction with treatment and consists (in version II) of eleven multiple-choice items across four domains (see also Section 8.5.1.5 in Protocol).

The items are summed up domain-wise to derive domain scores, which are then transformed to a 0 to 100 scale. A score can only be computed for a domain if no more than one item is missing from that domain. An overall score is not defined. The scores will be derived for baseline, Day 90 and EOT/EOS (Day 360). All analyses will be performed by domain.

The higher the values, the higher is the participant's satisfaction with the treatment.

CCI

2.9.4 Walking Impairment Questionnaire

The (modified) Walking Impairment Questionnaire (WIQ) is used to assess participants walking distance, speed, and stair climbing ability and records 16 items in four categories (see also Section 8.5.1.6 in Protocol). The WIQ will only be provided to the PAD subset.

The graded scores in three of the four categories (distance, speed, stair climbing) are multiplied by a pre-specified weight for each category (see corresponding Manual), then summed up and divided by the maximal score possible to derive the final category-specific scores ranging from 0 to 100 % for baseline, Day 90 and EOT/EOS (Day 360). An overall score and a score for the fourth category (pain) is not defined. All analyses will be performed by domain score.

If there is missing data for a participant and the available data is more than 50% for the corresponding category, the maximal score possible will be adapted for this category. No imputation will be done. If less than 50% of the items are non-missing the category-specific score will be excluded from the analysis.

The higher the values, the better is the participant's condition.

CCI

2.9.5 MacNew Heart Disease Quality of Life Questionnaire

The MacNew Heart Disease Quality of Life Questionnaire (MacNew) is used to assess the quality of life of participants with cardiovascular diseases and covers the query period of the

past 14 days (see also Section 8.5.1.7 in Protocol). It consists of 27 items across three overlapping domains. The MacNew will only be provided to the AP subset.

The scores of the three domains (physical limitations, emotional and social function) are calculated by averaging the point values in the associated items. The average value of all 27 items gives the global total score. The score will be derived for baseline, Day 90 and EOT/EOS (Day 360). If not specified otherwise all analyses will be performed for total and domain scores.

Missing responses do not contribute to the score - also no imputation will be done. If less than 50% of the items for the corresponding domain is missing, the domain score will be excluded from the analysis (see corresponding Manual).

The higher the score(s), the better ist the participant's quality of life.

CCI

2.9.6

CCI

CCI

2.9.7

CCI

CCI

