2.9.2 Gastrointestinal Symptom Rating Scale

The self-administered Gastrointestinal Symptom Rating Scale (GSRS) questionnaire contains 15 items for gastrointestinal syndromes, which are composed of 5 dimensions (abdominal pain, reflux syndrome, indigestion, diarrhea and constipation) and uses a Likert scale with 7 units from 1 to 7 (no discomfort to very severe discomfort, see also Section 8.5.1.4 in Protocol)

The subscores of individual domains are calculated by averaging the scores of the associated items. The average of all subscores gives the total score, which ranges between 1 and 7. The score will be derived for each visit between baseline and EOT/EOS (Day 360).

If there is missing data for a participant and the available data is more than 50% for the corresponding dimension, the missing items will be imputed using the mean score of the non-missing item scores. Else no imputation will be done and the dimension score will be excluded from the analysis (see corresponding Manual).

The lower the value, the better the gastrointestinal condition.

CCI

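### The MacNew missing-item rule in SAP 2.9.5 is reversed for domain scores: complete domains are excluded and domains at least half empty are kept

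*SAP*

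**What the plan says.** SAP 2.9.5 describes the instrument and its scoring. On structure: "It consists of 27 items across three overlapping domains". Each domain score is the mean of its items, and for the total, "The average value of all 27 items gives the global total score". Analyses are planned for both total and domain scores unless stated otherwise.

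On missing items it says "Missing responses do not contribute to the score - also no imputation will be done", and then: "If less than 50% of the items for the corresponding domain is missing, the domain score will be excluded from the analysis". That sentence ends with a reference to the questionnaire's manual, which is not among the documents.

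Protocol 8.5.1.7 gives the averaging but no missing-item rule. SAP section 4, which lists departures from the protocol's analyses, does not mention MacNew. SAP 2.9 classes MacNew as exploratory and states that the pre-processing of each questionnaire is described in the sections that follow, so 2.9.5 is the operative scoring instruction.

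**The concern.** A missing-item threshold exists to stop a score being built from too few answers. This one does the opposite. Read as written, it removes the domain scores that are fully or mostly answered and keeps those resting on half or fewer of their items.

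A programmer has two options. One is to follow the text, which produces domain-score tables made up only of poorly completed domains. The other is to depart from the SAP without a documented basis. The second is the likelier outcome, but a choice about which data to include should be on record before treatment codes are known. MacNew is the heart-disease-specific quality-of-life instrument for the angina subset, which protocol section 5 names as a group where benefit is thought especially likely.

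**Working it through.** No sample size, power or error rate is involved, so the check is one of logic, followed by a comparison with the other questionnaires.

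**Step 1: the rule as written.** Let a domain have *k* items, of which *m* are missing. SAP 2.9.5 excludes the score when *m/k* < 0.5 and therefore keeps it when *m/k* ≥ 0.5.

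- *m* = 0: 0/*k* = 0 < 0.5, so a complete domain is excluded.
- *m* = *k*: the rule would keep the domain, but there is nothing to average.

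This holds for any *k*, so it does not matter that the documents give no item count per domain.

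**Step 2: illustration.** Take *k* = 27, the full item count, purely to show the cut. 13/27 = 48.1% and 14/27 = 51.9%.

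| Items missing | As written | Direction reversed |
|---|---|---|
| 0 to 13 | excluded | scored |
| 14 to 26 | scored | excluded |
| 27 | no score possible | excluded |

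**Step 3: the other missing-item rules in the SAP.**

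| Questionnaire (SAP section) | Rule | Favours |
|---|---|---|
| WIQ (2.9.4) | "If less than 50% of the items are non-missing the category-specific score will be excluded from the analysis" | more complete |
| GSRS (2.9.2) | Missing items are filled if "the available data is more than 50% for the corresponding dimension"; otherwise "Else no imputation will be done and the dimension score will be excluded from the analysis" | more complete |
| SF-BPI (2.6.2.4) | Missing items are filled only if more than half are available (3 of 4, or 4 of 7); otherwise the domain score goes to the general missing-data method | more complete |
| TSQM (2.9.3) | Scored only if at most one item of the domain is missing | more complete |
| MacNew (2.9.5) | Excluded if less than half are missing | **less complete** |

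The MacNew sentence is close to the WIQ sentence with the negation lost. Four rules run one way and one runs the other, with no reason given for the difference.

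**Step 4: the boundary.** The other rules do not settle what happens at exactly half. GSRS requires more than half available, so exactly half is excluded. SF-BPI does not fill items at 2 of 4. WIQ scores above half and excludes below half, leaving exactly half undefined. Only the manual can decide this for MacNew.

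**Step 5: reach.** The exclusion sentence refers to domain scores only. The global score is defined separately and has no stated threshold. MacNew is not among hypotheses H01 to H06 in SAP 2.6.2.5.

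**The case against.** The strongest reply is that this is a slip of one word with an obvious meaning. The preceding sentence and the WIQ and GSRS rules show what was intended, and the reference to the manual gives the programmer another source. The questionnaires are completed on an electronic handheld and checked by site staff for completeness (protocol 8.5.1). Literal coding would therefore probably give almost empty domain-score tables, and someone would notice before reporting. The endpoint is exploratory and limited to a subset.

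Most of that stands, and it is why the point is minor. It does not remove the point. The sentence is the scoring instruction, nothing visible in either document corrects it, and the manual cannot be consulted here. Some text later in 2.9.5 is redacted, but the rule is complete without it.

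A reader might infer more than the documents support:

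- *That every complete questionnaire is lost.* It is not. A complete form still contributes its global score even under the literal rule.
- *That the trial's quality-of-life conclusions are at risk.* The secondary quality-of-life objective is pain-related and measured by the SF-BPI, whose missing-item rule runs in the right direction.
- *That a given share of the data would be discarded.* The documents report no completion rates and no size for the angina set, so any percentage would be an assumption.

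**Conclusion.** The rule is wrong as written and should be corrected. Followed literally, it excludes every MacNew domain score with less than half of its items missing, complete domains included, and keeps those at least half empty.

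The effect is confined to the three domain scores of one exploratory instrument in the angina set. The global score, the primary analysis and the confirmatory secondary analyses are unaffected. How many scores are involved cannot be estimated from the documents.

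The finding that the rule is reversed rests on the sentence itself and on the four rules that run the other way, and needs no numerical assumption. The one thing that cannot be confirmed is the manual's exact threshold, including how it treats a domain with exactly half its items missing. Severity: minor but real.

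**What to change.** Before unblinding, change the sentence in SAP 2.9.5 so that it runs in the same direction as the WIQ rule, for example: *A domain score is excluded from the analysis when fewer than half of that domain's items are non-missing.* As worded, this would score a domain with exactly half its items answered, so check that case against the cited manual and state it explicitly.

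While the section is open, the sponsor could also record whether the manual sets any minimum number of answered items for the 27-item global score. The SAP gives none, and the documents offer no basis for proposing a value.

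The cost is one sentence in the SAP and a check of the domain-score derivation. No new data are needed and no other analysis changes.

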2.10 Biomarkers

Summary statistics will be provided by treatment and visit/time for Lp(a) and Apo B. PCSK9 levels will remain blinded until unblinding.

2.11 Other Exploratory analyses

2.11.1 CCI

CCI

2.11.2 CCI

CCI

CCI

2.11.3 CCI

CCI

2.12 Interim analysis

Not applicable.

3 Sample size calculation

3.1 Primary endpoint(s)

The assumption for the occurrence of LDL-C target attainment on day 90 in the inclisiran-arm is based on the ORION study data set. In CCI of participants achieved an LDL-C level CCI mg/dL target at day 90 CCI (Ray et al., 2020). In CCI of participants achieved an LDL-C level CCI mg/dL at day 90 CCI (Ray et al., 2020). Assuming CCI, approx. CCI of participants achieve their individual LDL-C target at day 90. For the assumption of LDL-C target attainment at day 90 in the placebo arm, the EXPLORER trial reports response rates for CCI (Ballantyne et al., 2007): CCI of participants achieved an LDL-C level CCI mg/dL at day CCI. Mean LDL-C level at day CCI was CCI, so it can be estimated that approx. CCI of participants may have reached the CCI target. Based on the study population and treatment regime herein, day CCI of EXPLORER trial likely relates to day 90 of the present study. With the above stated assumption of a CCI among the participant population, CCI of participants are considered to reach their LDL-C target at day 90. Considering the high LDL-C levels at baseline in the EXPLORER trial compared to ORION trials, herein, a slightly higher goal attainment rate of approx. CCI at day 90 for participants in the comparator arm is assumed. Under these assumptions, CCI participants per arm are required based on a chi-squared test of proportions to achieve 90% power on a two-sided, 5% significance level. In order to compensate for missing values and other protocol deviations, approximately 880 participants per arm (approximately 1760 participants in total) should be enrolled/randomized into this trial.

3.2 Secondary endpoint(s)

For the secondary endpoint “Proportion of participants experiencing at least one muscle-related AE as defined in the SMQ rhabdomyolysis / myopathy from day 1 to day 360”, the following deliberations apply: Due to the potent LDL-C lowering effect of inclisiran and the CCI

CCI in both treatment-arms depending on the achievement of the individual LDL-C target of the participant, it is expected that the mean and the median statin doses will be CCI. Based on the CCI of action of inclisiran, it is estimated that the CCI of participants in the CCI will require CCI rosuvastatin CCI in the treatment period. Thus, most participants in the CCI will remain on the lower doses of rosuvastatin throughout the trial. In contrast, in the CCI, most participants will require CCI of rosuvastatin CCI to sufficiently lower the LDL-C.

Various studies have shown that statins at high dosages are associated with CCI ranging between CCI for atorvastatin 80 mg/day (Parker et al., 2013) to CCI for various statins (Bruckert et al., 2005), while there is evidence from double-blind clinical trials that CCI statins are not associated with a CCI than placebo with an overall incidence of CCI (Gupta et al., 2017). For the sample size calculation, we assume a rather conservative approach of an occurrence of CCI in the CCI and CCI in the CCI. Pain can be of different CCI. Assuming CCI are CCI in a conservative approach, according to the methodology defined CCI to CCI AEs will only be CCI, if the CCI interval of the risk ratio stays below the threshold of CCI. A sample size of CCI participants per arm will result in 90% power to obtain a confidence interval of the risk ratio fulfilling this condition. For a considerable additional benefit, the respective threshold is defined by the CCI. Under the assumptions above, the power to meet this condition as well would be CCI. The power calculations were performed with SAS Software by simulating and analyzing 1000 studies with the assumed AE rates.

4 Change to protocol specified analyses

Null hypothesis for primary and secondary endpoints will be rejected as described in the testing strategy in SAP section 2.6.2.5 and protocol section 12.5.1. There is contradictory information given for the respective endpoints in protocol section 12.5.2 with regard to p-values and alpha level. This contradictory information will not be considered for the analyses and control of familywise type I error rate will be followed.

Analysis of adverse events will be done for TEAEs. Protocol section 12.5.3 describes that additionally, all summary tables for AEs will be repeated for on-treatment AEs only (TEAEs). This repetition will not be done.

First dose of double-blind treatment (Day 1) will be considered for the analyses, even if protocol mentions time of randomization. Day 1 and randomization date of some participants may not be the same, therefore Day 1 is considered for consistency of the analyses.

There will not be a separate table for exclusions from the analyses set, as there are no PDs defined excluding participants from an analysis set and exclusions are covered by the definition of the analyses set. Therefore, analysis would be redundant with other tables.

Region and country will not be summarized for the randomized set, countries are summarized on the FAS.

Supplementary analyses presenting relative risk and risk difference will be presented using CMH with Mantel-Haenszel estimators for both measures and will not be based on score statistics.

Descriptive summary of all vital signs data will not be provided, number and percentages of participants with notable abnormal vital signs will be provided instead. Listing of vital signs will be limited to the notable abnormal vital signs.

5 Appendix

5.1 Imputation rules

Any date incompletely reported is split into its day, month, and year components. In SAS, a numerical date value can only be defined if all these date components are known; incomplete dates are to be handled as text strings (character-type variables); as such, they could not be easily processed. An imputation rule for incomplete dates will be performed.

5.1.1 Blinded investigational treatment

The blinded investigational treatment administration date should be complete since it is injected at the study site. In case of missing or partial missing dates, the visit date will be used as the blinded investigational treatment administration date.

5.1.2 AE and hospitalization date imputation

The partially missing AE and hospitalization start/end date will be imputed. Completely missing start and end dates will not be imputed. If imputed date is after the EOS/EOT date, EOS/EOT date will be used instead. If imputed date is after the date of death, date of death will be used instead. Details will be provided in the study Programming Dataset Specification (PDS).

5.1.3 Concomitant medication date imputation

The partially missing concomitant medication start/end date will be imputed. Completely missing start and end dates will not be imputed. If the imputed date is after the EOS/EOT date, EOS/EOT date will be used instead. If imputed date is after the date of death, date of death will be used instead. Details will be provided in the study PDS.

5.1.4 Other missing dates

If other dates (e.g. medical history, procedures) are partially missing, details for imputation will be provided in the study PDS.

5.2 Stratification

The stratification factor is given by the CV risk group as defined in the following:

- Very high risk participants with at least one the following:
 1. Documented ASCVD
 - ACS: Unstable angina or myocardial infarction

- Stable angina
 - Coronary revascularization
 - Unequivocally documented ASCVD
 - Stroke and TIA
 - PAD
2. Diabetes mellitus (DM) with target organ damage (defined as microalbuminuria, retinopathy, or neuropathy), or at least ≥ 3 major risk factors, or early onset of Type 1 DM of long duration (< 20 years)
 3. A calculated SCORE $\geq 10\%$ for 10-year risk of fatal CVD
 4. Pre-existing diagnosis of heterozygous familial hypercholesterolemia (HeFH) with ASCVD or with another major risk factor.
- High risk participants with at least one of the following:
 1. Markedly elevated single risk factors, in particular triglycerides > 8 mmol/L (> 310 mg/dL), LDL-C > 4.9 mmol/L (> 190 mg/dL), or blood pressure $\geq 180/110$ mmHg
 2. Pre-existing diagnosis of HeFH without other major risk factors
 3. DM without target organ damage (defined as microalbuminuria, retinopathy, or neuropathy), with DM duration ≥ 10 years or other additional risk factor
 4. Moderate chronic kidney disease (eGFR 30-59 mL/min/1.73m²)
 5. A calculated SCORE $\geq 5\%$ and $< 10\%$ for 10-year risk of fatal CVD as defined by the cardiovascular risk categories in the 2019 ESC/EAS guideline ([Mach et al 2020](#)).

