5.1 Inclusion criteria

Participants eligible for inclusion in this study must meet **all** of the following criteria:

At Screening:

1. Written informed consent must be obtained before any assessment is performed.
2. Male or female participants ≥ 18 years of age.
3. Participants categorized as very high or high CV risk, as defined below:
 - **Very high risk participants** with at least one of the following:
 1. Documented ASCVD
 - ACS: Unstable angina or myocardial infarction
 - Stable angina
 - Coronary revascularization
 - Unequivocally documented ASCVD upon prior imaging
 - Stroke and Transient Ischaemic Attack (TIA)
 - PAD
 2. Diabetes mellitus (DM) with target organ damage (defined as microalbuminuria, retinopathy, or neuropathy), or at least ≥ 3 major risk factors, or early onset of Type 1 DM of long duration (> 20 years)
 3. A calculated SCORE2 $\geq 7.5\%$ for age < 50 years; SCORE2 $\geq 10\%$ for age 50-69 years; SCORE2-OP $\geq 15\%$ for age ≥ 70 years to estimate 10-year risk of fatal and non-fatal CVD

4. Pre-existing diagnosis of heterozygous familial hypercholesterolemia (HeFH) with ASCVD or with another major risk factor.

OR

- **High risk participants** with at least one of the following:
 1. Markedly elevated single risk factors, in particular total cholesterol > 310 mg/dL, LDL-C > 190 mg/dL, or blood pressure \geq 180/110 mmHg
 2. Pre-existing diagnosis of HeFH without other major risk factors
 3. DM without target organ damage (defined as microalbuminuria, retinopathy, or neuropathy), with DM duration \geq 10 years or other additional risk factor
 4. Moderate chronic kidney disease (eGFR 30-59 mL/min/1.73m²)
 5. A calculated SCORE2 2.5 to <7.5% for age under 50 years; SCORE2 5 to <10% for age 50-69 years; SCORE2-OP 7.5 to <15% for age \geq 70 years to estimate 10-year risk of fatal and non-fatal CVD

as defined by the cardiovascular risk categories in the 2019 ESC/EAS guideline ([Mach et al 2020](#)), [Note: Table 4, page 15: High risk and very high risk only] and updated SCORE2 and SCORE2-OP (according to [Hageman et al 2021](#), [de Vries et al 2021](#), [Visseren et al 2021](#)). Further details for documented ASCVD are provided in [Section 16.4](#).

4. LDL-C levels:
 - a. in participants with very high cardiovascular risk: serum LDL-C \geq 55 mg/dL.
 - b. in participants with high cardiovascular risk: serum LDL-C \geq 70 mg/dL

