2.1.1.8 Cardiovascular risk category

Randomization was stratified by cardiovascular (CV) risk category ("very high" and "high").

The stratification of "high" and "very high" for cardiovascular risk used in the statistical analysis will be programmatically derived based on eCRF data as the last assessment of CV risk prior to first dose of double-blind treatment. The stratification factor recorded at randomization will not be used in the statistical analysis. Strata recorded in the IRT data, and derived strata (from data reported on the eCRF) will be listed and flagged if discrepant.

Whenever "CV risk category" is mentioned throughout the remainder of this document, this refers to the derived CV risk category prior to first dose of double-blind treatment, if not specified otherwise.

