2.5.1 Primary endpoint(s)

The primary endpoint for this study is the proportion of participants at Day 90 achieving their individual LDL-C target of less than 55 mg/dL or less than 70 mg/dL, i.e. <55 mg/dL for participants with very high cardiovascular risk and <70 mg/dL for participants with high cardiovascular risk. The participant-individual LDL-C target depends on their cardiovascular risk category at time of the LDL-C measurement and will be evaluated according to the most recent assessment of CV risk as determined by the investigator. Accordingly, the achievement of the participant-individual LDL-C target forms a binary response variable for LDL-C target ("achieved"/"not-achieved") and will be analyzed in the FAS.

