5.5 Statistical models

5.5.1 Analysis supporting primary objective(s)

5.5.1.1 (Binary) Logistic regression

The primary endpoint will be analyzed using a binary logistic regression of the following form:

$$\text{logit}(LDL \leq LDL \text{ target}) = \text{treatment} + CV \text{ risk category}.$$

In SAS the PROC LOGISTIC procedure will be therefore used. The ODDSRATIO statement will be used to estimate the odds ratio. The E option will be used to obtain a table of coefficients of the linear combination of parameters that define the log odds for each treatment group. Odds

ratios will be presented with associated two-sided 95% confidence interval for treatment comparison.

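### SAP 5.2 defines the CV-risk strata with criteria that contradict protocol 5.1, and SAP 5.5.1.1 counts LDL-C exactly at target as success; both need correcting, although the strata are affected only if 5.2 is programmed literally

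*SAP*

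**What the plan says.** SAP 5.2 is written as a definition: "The stratification factor is given by the CV risk group as defined in the following". For very high risk it includes "early onset of Type 1 DM of long duration (< 20 years"; for high risk it includes "in particular triglycerides > 8 mmol/L (> 310 mg/dL". Its risk-score criteria are SCORE of at least 10%, and of 5% to below 10%, for 10-year fatal CVD.

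Protocol 5.1 has "early onset of Type 1 DM of long duration (> 20 years" and "in particular total cholesterol > 310 mg/dL". Its risk-score criteria use SCORE2 and SCORE2-OP for fatal and non-fatal CVD, with separate cut-offs for ages below 50, 50 to 69, and 70 or older.

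SAP 2.1.1.8 says the analysis stratum is derived programmatically from the eCRF, as the last CV risk assessment before first dose. It adds: "The stratification factor recorded at randomization will not be used in the statistical analysis".

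On the response itself, SAP 2.5.1 defines success as "achieving their individual LDL-C target of less than 55 mg/dL or less than 70 mg/dL". SAP 5.5.1.1 introduces the model with "The primary endpoint will be analyzed using a binary logistic regression of the following form" and then writes the modelled event as LDL ≤ LDL target.

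**The concern.** The SAP states that it rests on protocol version 03, and its section 4 lists departures from the protocol. None of the three differences appears there, so they read as errors and not as decisions. SAP 5.2 is the only list of risk criteria in the SAP. A programmer told to derive the factor from eCRF data could reasonably take 5.2 as the rule.

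The factor has wide reach. CV risk category enters the primary logistic model, the imputation models, the Cochran-Mantel-Haenszel strata, the repeated-measures models, the pain-day model, the ANCOVA and Cox models, and the subgroup analyses. If it were rebuilt from 5.2, the risk subgroups would not be the protocol's groups, and the listing that flags discrepancies against the IRT stratum would contain spurious flags.

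The inequality in 5.5.1.1 matters in a different way. It concerns the primary response and does not depend on how the stratum is obtained.

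**Working it through.** **Step 1. Criteria side by side**

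| Criterion | Protocol 5.1 | SAP 5.2 |
|---|---|---|
| Risk score | SCORE2 / SCORE2-OP, fatal and non-fatal | SCORE, fatal only |
| Very high cut-off | 7.5% (<50 y), 10% (50–69 y), 15% (≥70 y) | 10%, all ages |
| High band | 2.5 to <7.5%, 5 to <10%, 7.5 to <15% (same age bands) | 5 to <10%, all ages |
| Type 1 diabetes, early onset, long duration | >20 years | <20 years |
| Single lipid factor | total cholesterol >310 mg/dL | triglycerides >8 mmol/L (>310 mg/dL) |

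**Step 2. Unit check on the lipid line.** The LDL-C pair on the same SAP line gives 190 / 4.9 = 38.78 mg/dL per mmol/L. The pair labelled triglycerides gives 310 / 8 = 38.75, and 8 × 38.78 = 310.2. The numbers are cholesterol numbers under the wrong name. With a triglyceride factor of 88.5 to 88.6 (an assumption, not in the documents), 8 mmol/L would be 708 to 709 mg/dL. Protocol 5.1 requires fasting triglycerides below 400 mg/dL, so on that factor no eligible participant could exceed 8 mmol/L at entry, though some could exceed 310 mg/dL.

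**Step 3. Effect of a literal reading of 5.2.**
- Type 1 diabetes: a participant who is very high risk only through more than 20 years' duration would lose that status. The SAP's own high-risk criterion (diabetes of at least 10 years without organ damage) would still place them in high risk. An early-onset case of under 20 years would move up to very high.
- Total cholesterol: a participant who is high risk only through this criterion would have no category.
- Risk score: no reclassification band can be read off, because SCORE and SCORE2 estimate different risks.
- Anyone who qualifies through a criterion common to both texts, such as ASCVD for very high risk, keeps at least that category.

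The documents give no count of participants who qualify only through the altered criteria.

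**Step 4. Where the factor comes from.** Protocol 8.2 has the investigator record the risk category itself in the eCRF. Protocol 12.5.2.2 takes the LDL-C targets directly from those entries. SAP 2.5.1 sets the responder target by the investigator's most recent assessment. If the recorded category is read, 5.2 plays no part.

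**Step 5. If misclassification did occur (illustration).** A large-sample logistic fit (treatment plus recorded stratum) assumed placebo response of 25% in very high risk and 40% in high risk, a very-high-risk share of 50% or 80%, and 5 to 20% non-differential misclassification. A true odds ratio of 1 stays at 1.00, 3 becomes 2.94 to 2.98, and 10 becomes 9.62 to 9.90.

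**Step 6. Results exactly on target.** Assumptions, none from the documents: baseline median 95 mg/dL with log-SD 0.30; residual log-SD 0.2 to 0.4; reductions of 50 to 55% on inclisiran and 10 to 25% on placebo; results in whole mg/dL. For target T and reduction r:

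share = Φ((ln(T + 0.5) − μ)/σ) − Φ((ln(T − 0.5) − μ)/σ), with μ = ln(95(1 − r)) and σ = √(0.30² + residual²).

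- Highest case: T = 55, σ = 0.361. Inclisiran (r = 0.50) 1.85%, placebo (r = 0.25) 1.55%, mean 1.70%. Of the 1776 randomized (protocol, Amendment 3 rationale), 0.0170 × 1776 ≈ 30.
- Lowest case: T = 70, σ = 0.50. Inclisiran (r = 0.55) 0.70%, placebo (r = 0.10) 1.05%, mean 0.88%, about 16 participants.

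Restricting baseline to values at or above target, as entry requires, gives about 0.9 to 1.75% (16 to 31 participants). Both arms gain responders, and the between-arm difference in the share that switches stays within about 1 percentage point either way.

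**The case against.** The strongest reply is that the SAP already defines the factor elsewhere. SAP 2.1.1.8 calls it the last CV risk assessment before first dose, and protocol 8.2 makes that a category chosen by the investigator under the protocol's criteria. No section says the category is rebuilt from components, and the protocol makes no provision for calculating the older fatal-event SCORE that a rebuild would need. The text in 5.2 looks carried over or mistyped: the lipid figures are cholesterol figures, and a long duration of under 20 years contradicts itself. The expression in 5.5.1.1 can be read as schematic notation, since SAP 2.5.1 and protocol 12.4.1 use a strict inequality.

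Most of this stands, and it rules out several stronger readings.
- A reader might infer that the factor is misclassified in every model. The documents do not support that, because the natural source is the recorded category.
- A reader might infer that the LDL-C targets would be wrong. They follow the investigator's latest assessment, not 5.2.
- A reader might apply the SAP's 5% and 10% cut-offs to SCORE2 values and list age bands that change category. That mixes two different scales.
- A reader might conclude that the IRT stratum must become the model factor. That does not follow from errors in 5.2. The IRT entry is made at screening, and a run-in of up to 120 days can come before first dose.

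What the reply does not remove is the wording itself. SAP 2.1.1.8 speaks of programmatic derivation, 5.2 presents itself as the definition, and neither says that the recorded category is taken as it stands. The inequality in 5.5.1.1 would give the wrong response if coded as printed.

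**Conclusion.** The point holds as two errors in the text, with different consequences.

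The three contradictions between SAP 5.2 and protocol 5.1 are certain. Their effect on the analysis is conditional: none if the investigator-recorded eCRF category is used, and an unknown number of misclassified participants if 5.2 is programmed. Even then, under the assumed rates in step 5, the null is preserved and the primary odds ratio moves slightly toward 1. The clearer harm would be to the risk-subgroup results and the IRT discrepancy listing.

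The inequality in SAP 5.5.1.1 contradicts SAP 2.5.1, protocol 12.4.1 and the inclusion criteria, which admit participants at exactly 55 or 70 mg/dL as not at target. Coded literally, it would turn roughly 1 to 2% of participants in total from failure to success, spread over both arms. That figure rests on the assumed distributions and on whole-mg/dL reporting; finer reporting would shrink it.

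**What to change.** 1. Replace the criteria in SAP 5.2 with those of protocol 5.1, or delete them and refer to that section.
2. State in SAP 2.1.1.8 that the factor is the last CV risk category recorded by the investigator in the eCRF before first dose, and that it is not recalculated from component criteria.
3. Change the expression in SAP 5.5.1.1 to LDL < LDL target.
4. Check that the programming specification agrees with items 2 and 3.

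An analysis using the IRT stratum is at most an optional sensitivity analysis. The cost is SAP wording and one specification check. It should be done before unblinding, because a later change to a model factor or to the primary response rule could look data-driven.
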